informed that tsDCS is an investigational technique that has been used in humans for other purposes, but this study will be the first to explore tsDCS as a potential treatment for major depressive disorder. It is expected that tsDCS will be effective and safe in treating depressive symptoms, while improving other aspects of brain-body communication as indicated by improvement in interoceptive awareness, anxiety and somatic symptoms, autonomic, and metabolic parameters.

Adverse events. As defined by the ICH and GCP guidelines, any untoward medical occurrence in a patient during the administration of the investigational procedure and which does not have a causal relationship with treatment will be considered an AE.

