Adverse events will be monitored during the study by the clinical research team, which includes Psychiatrists and a Neurologist and collectively have extensive experience conducting clinical investigation of mood disorders and in the case of [name], the use of transcutaneous spinal direct current stimulation for neurological rehabilitation. They also will be responsible for evaluating and documenting all adverse events during study visits or more frequently as necessary. Additionally, a study-related physician will be accessible by phone to patients 24 hours/day, 7 days/week during study participation. [name] and designated clinical researchers will be responsible for reviewing all laboratory and safety measures from all subjects following each visit. An adverse event (AE) is any unexpected medical occurrence in a patient or clinical investigation subject who is administered a product and which does not necessarily have a causal relationship with the treatment. This includes any clinical or laboratory change that occurs at any time following consent that does not typically occur in that subject and is considered clinically significant. The frequency and severity of all observed or volunteered AEs regardless of treatment group or suspected causal relationship to the study treatment will be recorded throughout the study. [name] and designated clinicians will also be responsible for determining causal relationships between the study treatment and all AEs. Withdrawal from the study as a result of an AE or because of therapeutic measures taken to treat an AE will be at the discretion of the PI. If a subject withdraws or is withdrawn from the study for any reason, a study physician will monitor subjects with any ongoing AE until the AE is resolved or determined to be stable. All AEs (including those present during screening) will be reported. However, for analytics purposes, only post-baseline (randomization) AEs (or AEs that are present at visit 1/ baseline but have increased in severity or frequency post-baseline) will be considered for calculating treatment group differences in AEs. All AEs will be reported to the study DSMB, and the IRB at the time of progress reports.

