A serious adverse event (SAE) is any adverse experience occurring during study participation that results in any of the following outcomes: death; a life threatening adverse drug experience; inpatient hospitalization or prolongation of existing hospitalization; a persistent or significant disability/incapacity; or a congenital anomaly/birth defect. Important medical events that may not result in death, be life-threatening, or require hospitalization may be considered serious adverse events when, based on appropriate medical judgment of the study physician, they may jeopardize the patient or subject and may require medical or surgical intervention to prevent one of the outcomes in this definition. The judgment of whether a particular AE meets the above criteria for an SAE for the proposed study will be determined by the PI, in conjunction with the proposed Data Safety Monitoring Board (DSMB). It will also be the PIs responsibility to manage all SAEs and to make referrals for appropriate care, as necessary. All SAEs will be reported to the University of Cincinnati Institutional Review Board and the study DSMB within 48 hours of their discovery. The study blind will be broken at any point throughout the study as needed to protect the safety of a subject. A person with the blinded information will be available 24 hours/day, 7 days/week if it is necessary to break the blind in an emergency situation. All subject information will be de-identified when reporting serious adverse events. All AEs and SAEs will be double entered into two separate databases (and checked for accuracy) that are de-identified and password protected to ensure confidentiality. [name] and the study team will ensure that all patients have appropriate follow-up care

options after their study participation, as previously described.

K. DATA AND SAMPLE STORAGE AND CONFIDENTIALITY.

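### Section F defines an adverse event as one that treatment did not cause, Section J defines it without regard to cause, and no text says which definition prevails

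*Combined protocol and SAP*

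**What the plan says.** Section F (Safety Measures), under Adverse events, gives a formal definition and attributes it to ICH and GCP. It says that an untoward occurrence "during the administration of the investigational procedure and which does not have a causal relationship with treatment will be considered an AE".

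Section J (Protection of Human Subjects) gives another. It starts from the kind of event: "An adverse event (AE) is any unexpected medical occurrence in a patient or clinical investigation subject who is administered a product". On causality, it describes the event as one "which does not necessarily have a causal relationship with the treatment". It adds: "This includes any clinical or laboratory change that occurs at any time following consent", provided that the change is not typical for that subject and is judged clinically significant.

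Section J then sets the working rules. AEs are captured "regardless of treatment group or suspected causal relationship to the study treatment will be recorded throughout the study", and designated clinicians determine the causal relationship for all of them. For the arm comparison, "for analytics purposes, only post-baseline (randomization) AEs", or AEs present at baseline that later worsen, "will be considered for calculating treatment group differences in AEs".

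Section E makes the difference in AE frequency between arms secondary outcome a. Section I compares those frequencies under Prediction 2, that active stimulation is safe and well tolerated. Section F, under Potential Risks, lists the known effects of the device: paresthesia, redness, itching and pain at the stimulated site.

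**The concern.** The two causality clauses are not loose paraphrases of each other. Section J's clause leaves causality open. Section F's clause, without the word *necessarily*, makes absence of a causal link a condition of being an AE. The events that say most about the safety of a new device would then fall outside the definition used to count them.

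If Section F were applied, the causality judgement would decide which events enter secondary outcome a. Events attributed to stimulation would leave the comparison by definition, and Prediction 2 would be tested on what remained. AEs are elicited by open-ended questions after each session (Section D.2), so staff need a written definition to classify what participants report. The one in the Safety Measures section is a natural place to look.

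**Working it through.** The documents state no figure on this point and no arithmetic applies. The check is to set the two definitions side by side and put test events through each.

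| Element | Section F, Adverse events | Section J |
|---|---|---|
| Kind of event | Untoward | Unexpected; includes changes atypical for the subject and clinically significant |
| Causality | Must not be caused by treatment | May or may not be caused by treatment |
| Timing | During administration of the procedure | Any time after consent |
| Recording rule | None | Record whatever the suspected cause |
| Rule for the arm comparison | None | Post-baseline onset or worsening; no causality filter |

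**Test event 1: redness under the electrode, judged to be caused by stimulation.** Section F: it has a causal relationship, so it is not an AE. Section J: causality does not matter, so it is not excluded on that ground, and it is recorded and enters the comparison if it arose after baseline. The answers are opposite.

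**Test event 2: an untoward event in week 4, judged unrelated to stimulation.** On causality it qualifies under both. The conflict is therefore confined to treatment-related events.

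**Which definition is intended?** Three features of Section J point to the neutral one. Recording ignores suspected cause. Clinicians must determine causality for all AEs, which would be pointless if a causal link disqualified an event. The arm comparison is restricted by onset or worsening only. Section F also lists the device's known side effects shortly before a definition that would exclude them. The likeliest explanation is that *necessarily* was left out of Section F.

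**Does any text give Section J precedence?** Section D.3 refers the reader to the Protection of Human Subjects section for details of the monitoring plan and the monitoring board. It does not say which AE definition governs.

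**Can the effect be sized?** No. The documents give no AE rate for either arm and do not say whether frequency is counted by participant or by event. The direction is open too. The sham procedure delivers short pulses at the start and end of each session (Section D.1.2), so site effects could occur in both arms, and study physicians are blinded to allocation (Section D.2).

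**The case against.** The strongest reply is that the working rules already settle the matter. Section F's definition is one sentence with no recording or analysis instruction, whereas Section J says what is recorded, who judges causality and what enters the comparison. This is a secondary outcome in an exploratory pilot of 20 participants. Most of that stands: it limits the practical risk and makes this a correction of wording, not a design fault. It does not remove the contradiction, because the formal definition in the safety section still says the opposite and nothing in the text subordinates it.

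A reader might also infer several stronger points that the documents do not support.

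- *Device-caused events will be dropped, and the arms will look falsely alike.* This follows only if Section F is applied. Even then, events could be dropped in either arm, so the direction is not fixed. With 10 per arm, one participant is 1/10, or 10 percentage points, of a per-participant rate. That is simple arithmetic on the arm size; it does not show how many participants would be affected.
- *The definitions also conflict materially on timing.* If Section F means the treatment course, the gap is only from consent to the first session. Randomization and the first session are both at visit 1, and Section J compares post-baseline AEs only, so the gap barely touches secondary outcome a. Reading Section F as session time alone fits poorly with an AE enquiry made after each session.
- *Section J's SAE definition is a third version.* It covers "A serious adverse event (SAE) is any adverse experience occurring during study participation" with specified outcomes. It defines serious events and imposes no causality condition.
- *Section J's word* unexpected *excludes the known site effects.* The text that follows speaks of changes atypical for that subject, so the word may mean unusual for the person and not absent from the device's known profile. The wording is loose enough to need reconciling, but it is not a clear exclusion.
- *Section F leaves site effects to the investigator's discretion.* That sentence follows a list of laboratory, ECG and examination assessments and most naturally refers to their results.

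**Conclusion.** Section F's AE definition is wrong as written. It contradicts Section J on causality and, taken literally, removes device-caused events from secondary outcome a and from the test of Prediction 2. The conflict is certain from the text. That it is a drafting slip is an inference, though a well-supported one.

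The consequence depends on which section staff follow. Under Section J, no event is lost on grounds of causality. Under Section F, all events attributed to stimulation are lost, by an amount and in a direction that the documents do not allow anyone to derive. The point should be corrected because it affects a stated safety outcome and costs almost nothing to put right. It gives no ground for saying that the AE comparison will in fact be biased.

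**What to change.** Replace the Section F definition with a single causality-neutral one and use the same words in Section J: any untoward medical occurrence in a participant after consent, whether or not related to the study treatment. Keep Section J's rule that only AEs arising or worsening after baseline enter the arm comparison.

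In the same edit, reconcile *untoward* in Section F with *unexpected* and the clinical-significance wording in Section J, so that the site effects listed under Potential Risks are counted in both arms.

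The cost is a wording edit to two sections, with no change to procedures, visits, sample size or analysis method. AE counts may be slightly higher than under the present wording.

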This is a study with a double-blinded, randomized, parallel group, sham controlled pilot clinical trial design. The protocol will be submitted to the Institutional Review Boards of the University of Cincinnati for review and approval. *This is a joint effort among basic and clinical researchers at the Lindner Center of Hope (a University of Cincinnati College of Medicine affiliate), the Department of Psychiatry and Behavioral Neuroscience and the Department of Neurology and Rehabilitation Medicine at the University of Cincinnati College of Medicine.*

Participants. Subjects will be recruited from the community and from the Lindner Center of Hope through advertising and word of mouth. Location: All study procedures involving participants will be conducted at the Lindner Center of HOPE. Inclusion criteria: 1) age 18-55 yrs., inclusive; 2) female or male; 3) BMI 18.5 to 35 kg/mts², inclusive; 4) current MDD episode diagnoses confirmed by Mini International Neuropsychiatric Interview (MINI) 5.0 with a duration of ≥1 month and ≤24 months; 5) moderate MDD symptoms according to Montgomery-Asberg Depression Rating Scale (MADRS) score ≥ 20 to ≤35; 6) no current or recent (past month) antidepressant pharmacological treatment; 7) GAD and other anxiety symptoms will be permitted; 8) using an effective contraceptive method (all participants of childbearing potential). Exclusion criteria: 1) Current or lifetime MDD episode non-responsive to two or more antidepressant treatments at adequate doses and time (including ECT); 2) Current or lifetime bipolar disorder or schizophrenia diagnosis; 3) current (past month): PTSD, psychotic or substance use disorder (nicotine and caffeine allowed); 4) significant risk of suicide according to CSSRS or clinical judgment, or suicidal behavior in the past year; 5) current chronic severe pain conditions; 6) current chronic use of: opioids analgesics, medications that affect blood pressure or drugs with significant autonomic effects (stimulants and antipsychotics allowed if dose stable for 1 month); 7) neurological, endocrinological, cardiovascular (including diagnosed hypertension) or other clinically significant medical conditions as judged by the clinician; 8) skin lesions on electrode placement region; 9) implanted electrical medical devices; 10) Pregnancy; 11) suspected IQ<80, and 12) any other clinically relevant reason as judged by the clinician.

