D.1.2. Spinal cord stimulator and stimulation protocol. The 2x2 Soterix® Medical transcutaneous spinal direct current stimulator model 0707-A device will be used. This is a tsDCS available only for investigational use, with which [name] has extensive experience and will provide appropriate training to the study team. This device will be appropriately labeled as an “Investigational Device. Federal (Law) limits device to investigational use”. The device will be kept in a secured area inside the LCOH Research Institute and will be made available only to trained personnel of the study team. This device allows anodal stimulation to be delivered at 2.5mA per 20-minute session or sham session consisting of short pulses (of the desired intensity) at the beginning and end of the sessions. This protocol of anodal stimulation has been reported to be effective in inhibiting ascending pathways with a lasting effect, to be safe and well under the threshold for tissue damage (77, 79). If stimulation intensity (in active or sham protocols) is not tolerable at 2.5mA, the clinician may decide to decrease intensity to 2.0 mA or 1.5 mA. If 1.5 mA stimulation intensity is not tolerated, the subject may be withdrawn from the study. If subject has tolerated a stimulation intensity of less than 2.5mA, the study clinician may attempt to increase the dose to 2.0mA or 2.5mA when considered clinically appropriate. An anode electrode (5x10cm) will be placed at the level of the 10th vertebrae spinal process. At this level, the current is expected to spread longitudinally through the spinal cord up to three additional vertebral levels (96). The cathode (5x7cm) electrode will be placed on the right shoulder over the deltoid area (78, 79, 97). Participants will be scheduled to receive sham or active tsDCS sessions three times/week. Subjects will be randomized in a 1:1 ratio using a simple allocation method to one of two experimental groups: 1) sham or 2) stimulation protocol. Randomization will be double-blinded. An independent operator (trained personnel from the research team) will prepare the tsDCS device parameters for each session, but will not participate in the rest of the assessments. Patients and raters will remain blinded to SCS protocol assigned to each participant throughout the study. During the session, subjects will remain in a calm and relaxing environment. All participants will be scheduled for the same procedures and number of scheduled visits during the eight-week follow-up period. (**Table 2**)

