Visit 0 (Screening). Subjects will be informed about study procedures and given a written informed consent to sign voluntarily before any study procedure is initiated (See Informed consent form attached to this protocol). Then, the clinical staff will evaluate the participant in order to obtain a psychiatric and medical history. The MINI will be used to confirm MDD diagnosis, the MADRS to evaluate depressive symptom severity and the CSSRS for suicidality. The clinical research team will perform a full neurological and physical evaluation, ECG, cardiovascular measurements, laboratory tests, urinalysis, urine drug test, and a blood pregnancy test (if applicable). After eligibility is confirmed, a baseline visit will be scheduled.

Visit 1 (Baseline). After verification of eligibility, subjects will be randomized to an “active” or to a “sham” tsDCS protocol. Treatment allocation will remain double-blinded throughout the study to raters and study physicians. A MADRS, CGI-S, CSSRS, PHQ-9, 4DSQ, BES and MAIA will be completed. BMI, waist and abdominal circumference, vital signs, blood sample and ECG will be obtained. A physical and neurological evaluation will be conducted. Participants will complete the ERT and SST prior and during the SCS protocol. Each participant will receive the assigned SCS protocol.

SCS sessions (1-24): Three tsDCS sessions per week will be scheduled. A CSSRS will be completed before each SCS session. Blood pressure and heart rate will be evaluated prior and after each tsDCS session. AE's will be assessed after each session through open-ended questions.

Full visits 2, 3, 4, and 5: A MADRS, CSSRS, CGI-S, CGI-I, PHQ-9, 4DSQ, BES and MAIA scales will be completed.

Anthropometric measures (Visit 3, 4, 5), vital signs, and ECG (Visit 4) will be obtained. A blood sample (visit 4), urine drug test (Visit 4) and pregnancy test will be performed if applicable (visit 4). A physical and neurological evaluation will be

conducted (Visit 3, 4, and 6). Participants will complete the ERT and SST prior and during the SCS protocol (Visit 4). Each participant will receive the respective tsDCS protocol. AE's will be recorded after each tsDCS session.

Full Visit 6 (Final visit): A MADRS, CSSRS, CGI-S, CGI-I, PHQ-9, 4DSQ, BES and MAIA scales will be completed.

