Primary Outcome: Difference in change from baseline to week 8 (or last available observation) in MADRS scores between active and sham tsDCS groups. **Secondary Outcome:** **a)** differences in AE's frequency between active and sham tsDCS groups, **b)** association between change from baseline to week 8 (or last available observation) in MADRS scores, and clinical (CGI-I, CGI-S, PHQ-9, MAIA, BES and 4DSQ), autonomic (BP, HR) and metabolic (anthropometric, adiponectin, leptin, cortisol, FGF-21 and LCn-3) parameter change from baseline to week 8(or last available observation), and **c)** MADRS sub-component (98) scores, clinical parameters (CGI-I, CGI-S, PHQ-9, MAIA, BES and 4DSQ), autonomic (BP, HR), and metabolic (anthropometric, adiponectin, leptin, cortisol, insulin, FGF-21 and LCn-3) parameters change from baseline to week 8 (or last available observation) difference between Active and Sham tsDCS groups. **Exploratory outcome measures:** **a)** difference in change from baseline to week 8 (or last available observation) in offline ERT and Stop signal task scores between active and sham tsDCS groups; and **b)** difference in change from baseline to week 8 (or last available observation) in offline and online change ERT and stop signal task scores between active and sham tsDCS groups

F. SAFETY MEASURES

Potential Risks. Safety evaluation will consist in recording all laboratory tests, vital signs and ECG results, suicidality monitoring (each SCS session), physical and neurological examinations and any adverse events (AE). As mentioned above, literature suggests that current density below 25 mA/cm² induces no tissue damage (99). Findings will be recorded as AEs at the discretion of the investigator. Known side effects to tsDCS are paresthesia, redness, itch, or pain in stimulated area. If they occur, these side effects tend to disappear within minutes to hours after stimulation. To our knowledge, no serious adverse effects have been reported with the use of transcutaneous direct current stimulation protocols using 2.5mA/cm² (100).

Risk/Benefit Assessment. Participants will be informed that there are other FDA approved treatment alternatives for major depressive disorder and that their participation in this study is voluntary. Therapeutic options include antidepressant medications, psychotherapy, invasive and non-invasive neuromodulation tools. Participants will also be

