
outcome and clinical trials studies. A study physician will work with the patient to arrange admission in the event that it is determined that a study participant needs psychiatric or medical hospitalization.

G. SAMPLE SIZE.

This is an exploratory pilot clinical trial for which up to 60 (including screen fails) participants will be screened in an effort to recruit 20 participants that will receive either sham (n=10) or active treatment (n=10) for 8 weeks. Recruitment efforts will be aimed at a 2 patient/month rate. The exploratory nature of the study precludes a sample size that would enable detection of small but still clinically relevant effects at conventional significance thresholds. However, estimates of effect sizes with confidence intervals will be useful as inputs to larger confirmatory studies if these effects fall in an appropriate range (i.e., at least moderate sample effect sizes of approximately 0.50 standard deviations), even if the conventional significance is not achieved.

H. FEASIBILITY OF RECRUITMENT AND RETENTION

Resources and Infrastructure: The University of Cincinnati (UC) College of Medicine, Department of Psychiatry was founded in 1932 and UC is the 14th largest recipient of NIH funding. Among departments of Psychiatry, UC has one of the largest psychopharmacology research programs in the United States dedicated to depression and bipolar disorder. The faculty has a long-term successful record of sustained research support related to mood, eating, and impulse control disorders and pharmacological treatments.

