Data management and analyses will be organized and performed by the research team under the guidance of [name], Director of the Division of Biostatistics in the Department of Psychiatry at the University of Cincinnati, who has participated in the development of this analytic plan. Data will be collected via Case Report Forms. The research coordinator will be responsible for managing the study flow, maintaining case report forms, and entry data into a password-protected database on REDcap.

Data Analysis. *Specific Aim 1: Prediction 1)* Active tsDCS treatment will result in a greater decrease in depressive symptom severity (MADRS) compared to Sham in adult patients diagnosed with MDD. *Efficacy:* Longitudinal effect of tsDCS will be assessed by comparing change in MADRS scores from baseline to week 8 (or last available observation). To take maximum advantage of intermediate observations while avoiding assumptions about the trajectory of change over time, we will use a repeated-measures ANOVA model (i.e., with time as a categorical variable), and the primary hypothesis test will be a planned contrast of the baseline-week 8 differences between groups. *Prediction 2)* Active tsDCS is safe and well tolerated in adult patients diagnosed with MDD. *Safety:* A similar analysis as used for efficacy data will be performed for laboratory assays, vital signs, anthropometric, clinical, autonomic and metabolic variables. Frequencies of AE's will be compared between groups using comparative analysis. *Specific Aim 2: Prediction 3)* Baseline and change in interoceptive awareness,

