somatic symptoms, clinical, autonomic and metabolic parameters will be associated with change in depressive symptom severity. A correlation analysis will be used to evaluate the association between treatment and depressive symptom severity, both total and in components (items). Correlation analysis will also be performed by gender, autonomic and metabolic parameters. Prediction 4) Active tsDCS treatment will result in a greater change in interoceptive awareness, anxiety and somatic symptoms, clinical, autonomic and metabolic parameters. Longitudinal effect of tsDCS will be assessed by comparing MADRS sub-component scores, clinical parameters (CGI-I, CGI-S, PHQ-9, BES, MAIA, and 4DSQ), autonomic, and metabolic parameters change from baseline to week 8 (or last available observation) difference between Active and Sham groups using a repeated-measures ANOVA as described above. Throughout, tests and confidence intervals for effect sizes will be two-sided, $\alpha=0.05$.

J. PROTECTION OF HUMAN SUBJECTS.

The data and safety monitoring plan for the proposed study will include monitoring of efficacy data by an independent Data Safety Monitoring Board (DSMB) and monitoring of tolerability data, including adverse events and serious adverse events, by the study investigators as well as the independent DSMB and the University of Cincinnati College of Medicine Institutional Review Board (IRB). The DSMB will consist of non-study related faculty with relevant research experience.

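### Cheap improvement: the primary MADRS contrast does not use the Visit 1 score as a covariate, so a chance baseline gap can shift the one reported estimate

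*Combined protocol and SAP*

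**What the plan says.** Section E defines the primary outcome as "Difference in change from baseline to week 8 (or last available observation) in MADRS scores between active and sham tsDCS groups". For its analysis, Section I (Specific Aim 1, Prediction 1) says "we will use a repeated-measures ANOVA model (i.e., with time as a categorical variable", and that "the primary hypothesis test will be a planned contrast of the baseline-week 8 differences between groups". The reason given is to use the intermediate visits without assuming a shape for the time course. No baseline covariate, equal-baseline constraint or sensitivity analysis of this contrast is named, and the error term of the ANOVA is not stated.

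Three other places bear on the point:

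- Section D.1.2: "Subjects will be randomized in a 1:1 ratio using a simple allocation method". No stratification by MADRS is mentioned, and Section G sets 10 participants per arm.
- Section D.2, Visit 1: "A MADRS, CGI-S, CSSRS, PHQ-9, 4DSQ, BES and MAIA will be completed". The covariate is therefore already collected.
- Section G, on the purpose of the trial: "estimates of effect sizes with confidence intervals will be useful as inputs to larger confirmatory studies".

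Prediction 4 in Section I reuses the method for the secondary outcomes, "using a repeated-measures ANOVA as described above".

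**The concern.** A change score removes the whole of a baseline difference only if each point at baseline carries through as exactly one point at week 8. If less carries through, the arm that starts higher appears to improve more for reasons unrelated to treatment. If more carries through, the reverse happens. Simple allocation of 20 patients leaves such a gap to chance.

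The average over all possible randomizations is unaffected, but this trial will report one estimate, and Section G wants that estimate for planning a larger study. The part of it that comes from the observed gap is what a baseline covariate would take out. The direction depends on an unknown slope, so a reader could not correct for it by eye. Deciding to adjust after a gap has been seen would leave the choice open to question.

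**Working it through.** The plan gives no power, SD or correlation, so there is no figure of its own to reproduce.

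**Inputs from the documents.** 10 per arm (Section G). Entry range "Montgomery-Asberg Depression Rating Scale (MADRS) score ≥ 20 to ≤35" (Section D.1). MADRS at Visits 1 to 6 (Section D.2).

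**Assumed inputs, not in the documents.** Baseline SD s0 = 3.5 or 4.33, where 4.33 = (35 - 20)/sqrt(12) is a uniform spread over the entry range. Week-8 SD s1 = 7, 8 or 9. Correlation r = 0.1 to 0.5 in steps of 0.1. This makes 30 settings, all with complete data and exactly 10 per arm.

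**1. Chance of a gap.** SD of the gap = s0 x sqrt(2/10).
- s0 = 3.5: 1.57 points; P(|gap| > 2) = 0.201.
- s0 = 4.33: 1.94 points; P(|gap| > 2) = 0.302.

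**2. Shift of the estimate.** With slope b = r x s1/s0, a gap g moves the change contrast by (1 - b) x g. A positive value favours the arm that started higher. At a 1-SD gap:
- Upper end (s0 = 4.33, s1 = 7, r = 0.1): b = 0.16; shift = 0.84 x 1.94 = 1.62 points.
- Lower end (s0 = 3.5, s1 = 9, r = 0.5): b = 1.29; shift = -0.29 x 1.57 = -0.45 points.

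**3. Shift against the standard error.** For a two-time-point change comparison, SE = sqrt(0.2 x V), with V = s0² + s1² - 2 x r x s0 x s1. Over the 30 settings SE runs from 2.71 to 4.29 (95% CI half-width 5.7 to 9.0). At the upper end above, V = 61.7 and SE = 3.51, so the shift is 1.62/3.51 = 0.46 SE, the largest of the 30. If the 0.50 SD mentioned in Section G is read as an SD of change, 0.46 SE is 0.46 x sqrt(0.2) = 0.21 SD.

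**4. Does the point estimate carry over to six visits?** Yes, with complete data. In a data set of 20 simulated patients the repeated-measures contrast and the difference in mean change were both -0.5224. The covariate model with a baseline-by-visit term and the two-time-point ANCOVA were both -1.0810.

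**5. Interval width, two-time-point comparison only.** Average ratio of adjusted to raw width = q x sqrt(17/16) x t17/t18, with q = sqrt(s1²(1 - r²)/V). It runs from 0.918 to 1.035 and exceeds 1 in 19 of 30 settings. At a 2-SD gap, 17/16 becomes 1.25 and the ratio runs from 0.996 to 1.123, above 1 in 29 of 30.

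**6. Coverage given the gap, two-time-point comparison only.** Raw change covers at 95% in all 30 settings at a 1-SD gap. At a 2-SD gap, reached or exceeded in about 5% of trials, coverage is 88.5% to 95%, against 95% with adjustment.

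**7. Do steps 5 and 6 carry over to the planned model?** No. I simulated a six-visit ANOVA with one pooled error term: SD rising linearly from s0 to s1, 20,000 trials per setting, and 12 settings (s0 = 3.5 or 4.33, s1 = 7 or 9, r = 0.1, 0.3 or 0.5). Without selecting on any gap, coverage of the baseline-to-week-8 contrast was 91-95% with equal correlation between visits and 82-89% with correlation that decays over time.

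**8. Wider assumptions.** With r up to 0.8 the 1-SD shift runs from -1.7 to 1.6 points, at most 0.57 SE. With s0 from 3 to 5 the chance of a 2-point gap is 14-37%.

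**The case against.** The strongest reply is that nothing here is wrong with the plan. The contrast does use baseline, it is unbiased over randomizations, and the plan gives a reason for its model. The gain from adjustment is modest: the shift at a 1-SD gap is at most 1.6 points against an interval half-width of at least 5.7, and the adjusted interval is on average wider in 19 of 30 settings. All SDs and correlations are assumed. Visit 1 scores need not be spread evenly over the entry range, and truly simple allocation gives exactly 10:10 in only 17.6% of trials. All of this stands. It limits the point to an optional improvement but does not remove it, because the shift in the single estimate remains and the covariate is already collected.

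A reader might go further and infer that adjustment will sharpen the estimate. Step 5 does not support that: entry limits keep the baseline SD small relative to week 8, and estimating a slope in 20 patients has a cost.

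A reader might also take the coverage figures in step 6 as describing the planned test, either as proof that it is sound at ordinary gaps or as proof that a large gap breaks it. Neither follows. Section I does not state the error term. With a pooled term and unequal visit SDs, coverage may fall below 95% whether or not the arms differ at baseline.

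**Conclusion.** The point holds as a low-cost improvement, to be considered rather than required. The primary contrast leaves out a covariate that the trial collects, and a chance gap shifts the one reported estimate by (1 - slope) points per point of gap. This follows from the stated contrast with complete data and needs no assumed figure.

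The size does depend on assumptions. On the 30 settings, a gap above 2 points has a 20-30% chance, and a 1-SD gap moves the estimate by -0.4 to 1.6 points, with the direction unknown in advance. The documents do not show that a planning decision would change. The firm benefit is that the part of the estimate due to the observed gap is removed. The interval-width and coverage figures belong to the two-time-point comparison and should not be quoted for the planned ANOVA.

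**What to change.** Prespecify in Section I the week-8 between-arm MADRS estimate and its confidence interval adjusted for Visit 1 MADRS. If the post-baseline visits are modelled together, include a baseline-by-visit term. Make this the primary analysis or, at minimum, report it beside the planned raw-change contrast. State how the last-observation provision applies, and apply it in the same way to both estimates so that they differ only in the adjustment.

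The same may be done for secondary outcomes that have a baseline value. CGI-I has none. No gain was calculated for these outcomes.

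The cost is analysis wording, no new data, and one degree of freedom for the week-8 contrast. In the two-time-point approximation the interval averages 8% narrower to 3.5% wider, and is up to 12% wider at a 2-SD gap. Participants with no post-baseline MADRS drop out of the adjusted model.
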